There are two specific *objectives*. First, assess and incorporate patients' post-operative pain experiences related to pelvic floor surgeries and identify what patients feel is important regarding pain experiences and expectations, their management and pre-operative education. Second, based on patient identified themes, assess the impact of patient-centered pre-operative education on 1) post-operative narcotic use and return to activities and function 2) patient preferences regarding amounts of post-operative narcotics prescribed and 3) to assess the impact on patient satisfaction and preparedness.

The *central hypothesis* is that the development of patient-centered, pre-operative education specifically addressing pain issues and narcotic prescribing practices will decrease post-operative narcotic use without curtailing return to normal activity or function. The *rationale* for this hypothesis is that existing evidence-based, post-operative pain guidelines lack requisite patient input and that aligning patient and surgeon goals prior to surgery will help manage post-operative pain expectations, reduce number of opioids prescribed, decrease risk of opioid dependence and improve patient satisfaction and preparedness. Obtaining proof that this approach is clinically feasible and beneficial would positively influence patient care. The central hypothesis will be tested with the following specific aims:

Specific Aim 1. 1a: To identify patient post-operative pain concerns surrounding pelvic floor surgery utilizing qualitative methodology through focus group sessions. 1b: To develop and implement pre-operative patient education based on the domains identified in specific aim 1a. Patient-centered education will address concerns regarding post-operative pain expectations and preferences regarding the amount of opioid prescribed at hospital discharge. *Hypothesis: Patients are concerned and apprehensive about post-operative pain related to surgery. The conceptual themes regarding pain issues can be incorporated into pre-operative patient education, expanding the patient role in decision-making regarding narcotics supplied at hospital discharge.*

Specific Aim 2. 2a: To randomize women undergoing pelvic floor surgery to standard pre-operative education versus patient-centered education (as determined by Aim 1) and evaluate whether patient-centered education, compared to routine education, decreases narcotic consumption without interfering with return to regular activity following hospital discharge. 2b: To test whether patient-centered education decreases the quantity of narcotics prescribed and/or increases patient satisfaction and preparedness. *Hypothesis: Patients exposed to patient-centered pre-operative education that includes pain expectations and patient preference, will decrease quantities of post-operative narcotics consumed and prescribed without interfering with return to activities, improving patient satisfaction and preparedness for surgery.*

Expected outcomes: Investigation of post-operative pain experiences in women who have undergone pelvic floor surgery will allow creation of patient-centered pre-operative educational material and allow inclusion of patients in the shared decision-making process. The resulting *positive impact* will be an improved approach to pre-operative education and management of post-operative pain in women undergoing pelvic floor surgery.

2. Background

Opioid use disorder has reached epidemic proportions in the United States. Opioid prescriptions per capita increased 7% from 2007-2012, with concomitant increases in narcotic associated emergency room visits and opioid-related deaths.¹ A Center for Disease Control (CDC) review reported that long-term opioid use disorder was commonly associated with narcotics prescribed for acute pain and that greater quantities at initial exposure were associated with greater risk of long-term use. Based on these findings, the CDC recommended limiting narcotic use for acute, non-surgical pain to ≤ 3 days.¹

There is currently no clear consensus regarding how narcotics should be prescribed for pain, including post-operative pain, which has resulted in over 800 pain-management guidelines.² Among these are two comprehensive, evidence-based documents cited by the CDC¹ that specifically address post-operative pain management.^{3,4} Those guidelines emphasize judicious post-operative narcotic prescribing practices, discouraging opioid misuse while encouraging return to function. The Washington Medical Directors Group⁴ provides particularly useful recommendations (Table 1). Perhaps the most important of which are 1) thorough pre-operative counseling, including setting realistic pre-operative expectations regarding post-operative pain and activity, and 2) optimizing non-narcotic analgesics allowing use of the lowest narcotic dose for the shortest duration of time (usually < 14 days).

There has been an absence of significant improvement in opioid prescribing practices despite increased attention to pain addiction issues.^{2,5} The large number of proposed guidelines and lack of consensus regarding their use, may contribute to inconsistent implementation of post-operative pain protocols in clinical practice.^{6,7} As surgeons, urogynecologists routinely prescribe narcotics for post-operative pain control. Consequently, we can play an important role in curbing the opioid epidemic in the patients we serve.

Urogynecologists lack a standardized approach to post-operative pain management. The ideal method to develop a standardized approach would be to bridge the gap between existing post-operative pain management options using a patient-centered approach. Our overarching goal is to provide pragmatic and replicable methods for post-operative pain management that can be disseminated for use by the urogynecologic community with potential use by the surgical community at large.

3. Study Design

This is a single-site mixed methods (qualitative and quantitative components) comprised of patient focus groups as well as a randomized control trial.

Aim 1 - Substantive data are lacking regarding patient experience and recommendations surrounding post-operative pain. In instances where little literature exists, utilizing qualitative methods can help identify and address patient concerns. We will create a semi-structured interview guide based on existing literature with known and perceived gaps. We will then conduct a minimum of four focus groups, recruiting patients who have undergone pelvic reconstructive surgery in the past 6 months to a year. Given our patient population, we will plan for 2-3 focus groups conducted in English and 1-2 focus groups conducted in Spanish. Based on internal practice data, approximately 15% of our patients

are primarily Spanish speaking. Including Spanish-speaking patients will improve the generalizability of this study since approximately 25% of Spanish-speakers in the US report that they speak minimal to no English.¹⁹ Based on prior experience we will recruit enough women to ensure each focus group has 5-10 participants per session. Our research team is bilingual with vast experience conducting and completing qualitative work.

Qualitative Analysis. According to the principals of grounded theory methodology, focus groups should be iterative, conducting additional sessions until saturation is reached. Saturation is met when no new concepts or themes are identified. Based on these principals and our past qualitative work, we will conduct a minimum of 4 focus group sessions and will continue to conduct sessions until saturation regarding post-operative themes is reached.²⁰⁻²² We will audio record each session. The recordings will then be de-identified, transcribed, reviewed, and coded to identify key words and phrases, which will then be grouped to form preliminary themes. Following each focus group session, the transcript will be reviewed and analyzed to identify additional themes and emerging concepts. We will revise the interview guide as needed prior to each successive focus group to ensure that all significant patient themes are identified and explored. Following completion of the sessions, identified themes will be organized into domains and used to create patient-centered education for Aim 2.

Aim 2 - This clinical trial will randomize women undergoing pelvic floor surgery to standardized routine pre-operative education versus standardized patient-centered pre-operative education (as identified in Aim 1) and will compare group differences for the following:

Outcome Measures

Primary Outcome: *1. Opioid Consumption* -- Opioid consumption determined by pill counts and translated into Morphine Milligram Equivalents (MMEs), within 2 weeks of hospital discharge. Patients will be required to bring their narcotic medications for pill counts at their routine 2-week follow-up appointment, since this is the most reliable method for checking opioid use. A medication diary will document pattern of opioid and non-narcotic use and may potentially serve as a behavioral modification tool for narcotic consumption.

Important Secondary Outcomes: *1. Opioids prescribed at hospital discharge and Opioids consumption at 6-week follow-up. 2. Patient Reported Outcomes Measurement*

Information Systems (PROMIS)²⁹ Physical Function SF & Pain Interference Questionnaires -- at baseline, 2 and 6 week follow-up. These validated questionnaires (available in English and Spanish) measure patient-reported physical activity and pain in the preceding 7 days.³⁰ Raw scores are translated into standardized scores; mean T-score represents the average score of the general population and a difference of 10 points represents 1 SD away from the mean.

Other Secondary Outcomes: *Patient Satisfaction and Preparedness for Surgery:* We will administer Global Questionnaires assessing (1) satisfaction with pre-operative education and care and (2) assessing patient's perceptions regarding preparedness for surgery.

These will be administered to both Spanish and English speaking patients. Questionnaires will be scored on a 1-5 Likert scale (Strongly disagree to Strongly agree). (Other validated post-operative satisfaction and preparedness questionnaires are not readily available in Spanish; existing Spanish questionnaires are condition-specific -- general or urogynecologic post-operative questionnaires are not currently validated.)

4. Inclusion and Exclusion Criteria

We will recruit women cared for by the University of New Mexico Urogynecology practice at UNMH Women's Care Clinic or Sandoval Regional Medical Center undergoing pelvic floor surgery. Patients who have elected to proceed will be offered study enrollment if they meet the inclusion and do not meet the exclusion criteria.

The *inclusion criteria* are:

1. Subjects are \geq 18 years of age
2. English or Spanish speaking
3. Patient scheduled for pelvic floor surgery

Exclusion criteria are as follows:

1. Unable to speak English or Spanish
2. Using long acting opioids (e.g. MS Contin, Fentanyl patch)
3. Primary or Pain Healthcare Provider recommends against study participation (eg. If the patient has a history of opioid use disorder or other confounding problems, we will contact the Primary Care Provider or Pain Healthcare Provider for their recommendations regarding study participation)
4. Undergoing surgeries that involve: Neuro/Interstim, Cysto/hyrdro distension, vaginal botox, mesh excision/complications

Special populations such as adults unable to consent, individuals who are not yet adults, pregnant women, and prisoners will not be included in this study.

We will be excluding women who are unable to speak and understand either English or Spanish. The justification for this is the satisfaction surveys are only available in English and Spanish and include the majority of the patients care by our group. Because these are our secondary objectives, it is important to use these standardized surveys. Additionally, we can only conduct focus groups in English or Spanish given our qualitative team is bilingual only in English and Spanish.

5. Number of Subjects

This a qualitative and randomized control trial at a single site – the University of New Mexico's Urogynecology department.

Up to 60 participants will be recruited for the focus groups and up to 198 people will be recruited for the randomized controlled trial at UNM.

Power Calculation & Statistical Analysis:

Based on our prior qualitative experience; approximately 10-12 participants must be recruited to have 6-8 attend the focus group. We plan to conduct 4 focus groups; and need to recruit 48 subjects. Given it is possible thematic saturation will not be achieved after 4 focus groups; we will recruit additional subjects and complete additional focus group until saturation is obtained. Although a few studies describe

opioid prescribing practices following Ob-Gyn surgery, we could not find any studies that reported opioid *consumption* following gynecologic or urogynecologic surgery. In order to perform the power calculations necessary for Specific Aim 2 (comparing opioid use between groups), because the actual number of opioids consumed following urogynecologic surgery is unknown, we will assume that patient-centered pre-operative education will result in a 33% decrease in narcotic consumption following hospital discharge compared to the control group. If we assume that controls consume a mean of fifteen 5 mg oxycodone pills (SD of +/-11 pills), and if we assume that the patient-centered group consumes 33% fewer pills (i.e. 10 pills in the modified education group), we would need a total of 152 participants (76 per group) to complete treatment and follow-up for a two-tailed t-test to have 80% power at $\alpha=0.05$. Assuming approximately 30% of patients will cancel surgery after randomization (including medical or insurance issues or change their mind) or will be lost to follow-up; we would need to enroll up to 198 women (99 per group) or until our designated power is met. We will perform between group comparisons using Chi-squared tests for categorical variables and t-tests for continuous variables. We anticipate that specific covariates (e.g. baseline questionnaire results, and narcotic use in last 3 months) may be confounders and that multivariable analyses will be required to evaluate the between group differences in outcomes. Note 1: When studies involve consent, an individual is considered a research subject once they have provided consent. If the research includes screening procedures after consent, please indicate the number of subjects that need to be recruited and the number that will actually participate in the research post-screening.

6. Study Timeline

Subjects in Aim 1 will participate in one focus group. Subjects in Aim 2 will participate up to the 6 week post-operative visit. This could occur within a window up of up to 8 weeks past their surgery.

We will be able to complete this project within the planned timeframe outlined below. The UNM Urogynecology Division performed approximately 230 major pelvic floor operations last year (average of 19/month). We will create the database, standardize current pre-operative sessions, and prepare the manual of operations and focus group script for Specific Aim 1 over the next 3 months. We will identify patients for enrollment in the focus groups during this initial period. This preparation will then allow us to successfully execute specific Aim 1 over the subsequent 3 months. We will have biweekly to weekly focus group meetings during the start-up period of the grant cycle. This allows 8-10 weeks to review our findings and develop a patient-centered educational plan. We will then enroll up to 198 women or until our specified power is met over the next 1-4 years given the halt of all elective surgeries with the Covid pandemic(averaging 11 participants/month). We anticipate finishing recruitment by October 2021 and follow up for those randomized by December 2021. We, thus, expect to meet our recruitment goals. The last 3 months of the grant cycle will be dedicated to statistical analysis and abstract and manuscript preparation. As all patients receive pre-operative education and have scheduled 2 and 6-week post-operative visits, we anticipate that the vast majority of our patients will be

willing and able to participate in this study. Experience indicates that our patients have willingly participated in previous RCTs with high retention rates. We expect that this pattern will continue. We will continuously evaluate our recruitment numbers.

Timeline	March-May 2018	June-August 2018	Sept 2018-December 2021 (3 years, 3 months)	December 2021-February 2022
IRB submission, Database creation, Focus group recruitment planned, Standardize patient-centered pre-operative education	↔			
Conduct focus group sessions, Standardize patient-centered pre-operative education		↔↔		
Recruit & follow 180 patients until 6-weeks after surgery			↔↔	
Data analysis, manuscript preparation				↔↔

7. Study Endpoints

Investigation of post-operative pain experiences in women who have undergone pelvic floor surgery will allow creation of patient-centered pre-operative educational material and allow inclusion of patients in the shared decision-making process. The resulting positive impact will be an improved approach to pre-operative education and management of post-operative pain in women undergoing pelvic floor surgery.

Primary Outcome: *1. Opioid Consumption* -- Opioid consumption determined by pill counts and translated into Morphine Milligram Equivalents (MMEs), within 2 weeks of hospital discharge. Patients will be required to bring their narcotic medications for pill counts at their routine 2-week follow-up appointment, since this is the most reliable method for checking opioid use. A medication diary will document pattern of opioid and non-narcotic use and may potentially serve as a behavioral modification tool for narcotic consumption.

Important Secondary Outcomes: *1. Opioids prescribed at hospital discharge and Opioids consumption at 6-week follow-up. 2. Patient Reported Outcomes Measurement Information Systems (PROMIS)²⁹ Physical Function SF & Pain Interference Questionnaires* – at baseline, 2 and 6 week follow-up. These validated questionnaires (available in English and Spanish) measure patient-reported physical activity and pain in the preceding 7 days.³⁰ Raw scores are translated into standardized scores; mean T-score represents the average score of the general population and a difference of 10 points represents 1 SD away from the mean.

Other Secondary Outcomes: *Patient Satisfaction and Preparedness for Surgery:* We will administer Global Questionnaires assessing (1) satisfaction with pre-operative education and care and (2) assessing patient's perceptions regarding preparedness for surgery.

These will be administered to both Spanish and English speaking patients. Questionnaires will be scored on a 1-5 Likert scale (Strongly disagree to Strongly agree). (Other validated post-operative satisfaction and preparedness questionnaires are not readily available in Spanish; existing Spanish questionnaires are condition-specific -- general or urogynecologic post-operative questionnaires are currently unavailable.)

8. Research Setting

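### The claim that opioid use falls without curtailing activity or function has no pre-specified criterion, and the planned difference tests could support it mainly through a non-significant result

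*Combined protocol and SAP*

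**What the plan says.** The opening objectives section states a two-part central hypothesis, that the education "will decrease post-operative narcotic use without curtailing return to normal activity or function", and says that the specific aims will test it. Specific Aim 2a asks whether the education "decreases narcotic consumption without interfering with return to regular activity following hospital discharge", and the Aim 2 hypothesis repeats the condition.

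Outcome Measures (section 3) and section 7 assign activity and function to secondary outcomes: PROMIS "Physical Function SF & Pain Interference Questionnaires -- at baseline, 2 and 6 week follow-up". These forms "measure patient-reported physical activity and pain in the preceding 7 days". The only numerical statement about them concerns scoring: "mean T-score represents the average score of the general population and a difference of 10 points represents 1 SD away from the mean".

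Sections 5 and 13 give the analysis: chi-squared tests for categorical variables and t-tests for continuous ones. Both sections expect that "specific covariates (e.g. baseline questionnaire results, and narcotic use in last 3 months) may be confounders". For that reason they foresee adjusted models as well: "multivariable analyses will be required to evaluate the between group differences in outcomes". Power is stated only for opioid pills. Section 5 requires 152 completers: "76 per group) to complete treatment and follow-up for a two-tailed t-test to have 80% power".

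**The concern.** Lower opioid use calls for a superiority test, and the plan has one. Preserved function is a claim that any loss is smaller than some tolerable amount, and a test of no difference does not address that. A significant improvement in function would settle the matter. Otherwise the only outcome of the planned tests compatible with the claim is a non-significant one, which may mean that function was preserved or that the trial was too small to show a loss.

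The planned analyses can produce confidence intervals. What is missing is a rule, fixed in advance, for reading them. Two scales at two post-operative visits give four candidate comparisons. Physical Function looks like the natural match for activity or function, but the plan does not say so, and it does not choose between week 2 and week 6. If the scale, visit and tolerable loss are settled after results are seen by arm, a claim of preserved function is open to challenge. Patients are not masked (section 28) and the scores are self-reported, which adds to the case for deciding early.

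**Working it through.** **Inputs from the documents.** 76 completers per group; two-sided alpha 0.05; opioid difference 5 pills with SD 11 (section 5). PROMIS scaling of 10 points to 1 SD in the general population (Outcome Measures).

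**Assumptions.** PROMIS SD in this trial 10, range 8 to 12; correlation between baseline and follow-up r = 0.5. True losses of 3, 4 and 5 points are illustrative. The documents give no trial SD, no correlation and no important difference.

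**Step 1: the plan's own figure.** n per group = 2 × (1.960 + 0.842)² × 11² / 5² = 2 × 7.849 × 4.84 = 75.98, so 76 per group and 152 in total. The plan's number is reproduced. It concerns opioid pills only.

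**Step 2: PROMIS precision at 76 per group, SD 10.**
- Unadjusted: SE = 10 × √(2/76) = 1.622. With 150 df the critical t is 1.976, so the 95% CI half-width is 1.976 × 1.622 = 3.2 points (2.6 to 3.8 for SD 8 to 12).
- Baseline-adjusted: residual SD = 10 × √(1 − 0.5²) = 8.66, SE = 1.405, 149 df. The half-width is 2.8 points (2.2 to 3.3).

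**Step 3: chance that a true loss is non-significant.** This is P(|T| < 1.976), where T is noncentral t with noncentrality loss/SE. For a 3-point loss the noncentrality is 3/1.622 = 1.85 unadjusted and 3/1.405 = 2.14 adjusted.

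| True loss (points) | Unadjusted, SD 10 (SD 8 to 12) | Adjusted, r = 0.5, SD 10 (SD 8 to 12) |
|---|---|---|
| 3 | 55% (37–67%) | 44% (24–58%) |
| 4 | 31% (14–47%) | 19% (6–35%) |
| 5 | 14% (3–28%) | 6% (1–16%) |

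**Step 4: sensitivity to numbers.** If 30% of the 198 enrolled are lost, 99 × 0.70 is about 69 per group. At SD 10 the rates for 3, 4 and 5 points become 58%, 36% and 17% unadjusted, and 48%, 23% and 8% adjusted.

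Each rate describes one comparison. If a true loss affected several of the four, the chance that all were non-significant would be lower. Selective choice among them would work the other way. Neither was computed.

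**The case against.** The strongest reply is that no wrong analysis is stated. A reader might infer that the investigators intend to report a non-significant PROMIS result as preserved function. The documents do not say that; they are silent on how such a result would be read. The second objective is only to assess the impact on narcotic use and return to activity, which estimates with intervals would satisfy. This limits the point to an unstated rule. It does not remove it, because the same section says that the two-part hypothesis will be tested.

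Second, PROMIS is secondary, and an unpowered secondary outcome is not in itself an error. The instruments, visits, scoring and baseline measurement are specified, and baseline questionnaire results are named as example covariates. All of this stands, and it limits the weight of the point.

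Third, a reader might infer that a non-significant result here would say nothing about function. That goes too far. At SD 10, a 5-point loss would be missed only 14% of the time, or 6% with adjustment. The weakness lies mainly in losses of about 3 to 4 points, and the documents do not say whether losses of that size matter.

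Fourth, choosing Physical Function as the single decisive scale is a judgement, since the plan lists both scales together. That is fair; what matters is that a choice is made and explained.

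**Conclusion.** The point holds and should be fixed. The second half of the central hypothesis has no margin, no interval rule and no decisive scale or visit, and the planned tests are not designed to show that function was preserved. That absence is certain from the text and depends on no assumption.

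The size of the consequence does depend on assumptions: a trial SD of 8 to 12, r = 0.5, and 76 completers per group. On these, non-significance is weak evidence against losses of about 3 to 4 points and considerably better evidence against a loss of 5. A reader might also infer that the trial's main result is compromised. The documents do not support that: opioid consumption is the sole primary outcome, and its comparison and its 152 completers are unaffected.

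**What to change.** Before outcomes are examined by arm, adopt one of two remedies of equal standing.

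- **(a) A criterion.** Name one decisive PROMIS scale and one visit, with reasons. Physical Function is the natural match. Week 2, with its 7-day recall, falls in the primary consumption window; week 6 addresses later return to activity. State a worsening margin in T-score points, justified on substance and not by what the sample can deliver. Conclude that activity was not interfered with only if the 95% CI for the baseline-adjusted between-arm difference excludes that margin. Report the other scale and visit as supportive, with CIs.
- **(b) Estimation only.** State that function will be estimated with 95% CIs and not claimed as preserved.

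Under either, do not read a non-significant difference as preserved function.

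To help choose: at 76 per group, SD 10 and no true difference, an illustrative 5-point margin would be excluded with probability 86.5% unadjusted and 94% adjusted, and a 4-point margin with probability 69% and 81%. If the justified margin is out of reach, (b) is the straightforward choice.

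The cost is analysis-plan wording. The scores are already scheduled, so no new data or visits are needed. The downside is that the preserved-function claim becomes harder to make, or is given up.

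### The only prescribing outcome stops at hospital discharge, while Aim 2b and its hypothesis have no such limit; later prescriptions go uncounted, so less prescribing cannot be told apart from deferred prescribing.

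*Combined protocol and SAP*

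**What the plan says.** Section 3 (Outcome Measures) and section 7 (Study Endpoints) list the same important secondary item: "Opioids prescribed at hospital discharge and Opioids consumption at 6-week follow-up". The prescribing half is fixed at discharge; only consumption extends to 6 weeks.

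The question to be answered is wider. Aim 2b reads "To test whether patient-centered education decreases the quantity of narcotics prescribed and/or increases patient satisfaction and preparedness". The Aim 2 hypothesis is that women given the patient-centered education "will decrease quantities of post-operative narcotics consumed and prescribed without interfering with return to activities". The second objective also speaks of "patient preferences regarding amounts of post-operative narcotics prescribed". None of the three stops at discharge.

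Section 6 sets the observation period: "Subjects in Aim 2 will participate up to the 6 week post-operative visit", with a window of up to 8 weeks after surgery.

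The text available mentions no refills, repeat prescriptions, outside prescribers or source for later prescriptions. The participant flow figure (Figure 1) and the removed pages could not be checked.

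**The concern.** The intervention includes shared decision making on the quantity of opioid prescribed (section 14), and patients are not masked (section 28). A smaller discharge supply in the intervention arm is therefore close to a record that the intervention was delivered. Whether less opioid was prescribed over the post-operative period also depends on what is prescribed after discharge, and no listed outcome measures that.

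On the prescribing outcome, a woman who leaves with fewer pills and later receives a further prescription counts the same as one who never needs more. The trial could then report reduced prescribing when part of the reduction was only postponed, and its data could not show whether this had happened. Section 14 argues that the intervention arm has less exposure to harm. As far as that rests on opioid supply, total supply is the relevant quantity.

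**Working it through.** **The plan's own figure.** The sample size rests on consumption: "controls consume a mean of fifteen 5 mg oxycodone pills (SD of +/-11 pills"), against 10 pills with the new education. For a two-sided 5% test with 80% power, n per group = 2 × (1.960 + 0.842)² × 11² / 5² ≈ 76, so 152 in total. This matches the plan. It concerns consumption, so nothing below changes it. The plan gives no figure for quantity prescribed.

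**Effect of leaving out later prescriptions.** Let C and T be the mean pills prescribed at discharge (control, intervention), R the refill size (taken as equal in both arms), and r_C and r_T the proportions refilled.

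- Discharge-only difference: C − T
- Total difference: (C + R·r_C) − (T + R·r_T) = (C − T) − R·(r_T − r_C)

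The sign of r_T − r_C sets the direction of any error in the absolute difference. If r_T is larger, the discharge-only difference is too big. If the two are equal, it is correct. If r_C is larger, it is too small.

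**Illustration.** The inputs are assumptions: C = 15 and T = 10, borrowed from the consumption assumption; R = 5, 10 or 15; refill rates chosen to cover all three cases. The discharge-only reduction is always 5/15 = 33.3%.

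| Refilled, control vs intervention | Total difference in pills (R = 5 / 10 / 15) | Reduction in total supply (R = 5 / 10 / 15) |
|---|---|---|
| 5% vs 5% | 5.00 / 5.00 / 5.00 | 32.8% / 32.3% / 31.7% |
| 10% vs 10% | 5.00 / 5.00 / 5.00 | 32.3% / 31.25% / 30.3% |
| 5% vs 20% | 4.25 / 3.50 / 2.75 | 27.9% / 22.6% / 17.5% |
| 10% vs 30% | 4.00 / 3.00 / 2.00 | 25.8% / 18.75% / 12.1% |
| 20% vs 10% | 5.50 / 6.00 / 6.50 | 34.4% / 35.3% / 36.1% |

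Example, third row with R = 10: control 15 + 10 × 0.05 = 15.5; intervention 10 + 10 × 0.20 = 12; difference 3.5; 3.5/15.5 = 22.6%.

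**Pill counts.** The primary outcome is "Opioid consumption determined by pill counts and translated into Morphine Milligram Equivalents (MMEs), within 2 weeks of hospital discharge". The plan does not state the starting quantity. Take 10 pills supplied, 10 more prescribed and 4 left at the visit. Counting from total supply gives 20 − 4 = 16 used; counting from the discharge supply gives 10 − 4 = 6. The starting quantity needs to be written down.

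**The case against.** The strongest reply is that the protocol treats prescribing as the discharge decision. Aim 1b says the education addresses "preferences regarding the amount of opioid prescribed at hospital discharge", and Aim 2 tests that education. Discharge quantity is then the most direct measure of the shared decision. This stands as a reason to keep it as a component. It does not make it an answer to Aim 2b and the hypothesis as they are worded.

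Second, the gap is partly covered. Consumption is measured at 2 and 6 weeks, two medication diaries are planned (section 22), and women bring their narcotic medications to the 2-week count, which is not confined to the discharge bottle. This stands for refill pills that are taken. The quantity prescribed after discharge is still not counted.

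Third, a reader might infer that discharge-only counting necessarily favours the intervention, because a smaller first supply must lead to more refills. The documents do not support that. They contain no refill data, and education that sets pain expectations and aims to lower use could also lower refill demand.

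Fourth, a reader might infer that the primary outcome undercounts opioid use in refilled women. The plan does not say the pill count starts from the discharge quantity alone; it only leaves the starting quantity unstated.

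**Conclusion.** The point holds as a gap between an aim and its outcome. Aim 2b and its hypothesis concern post-operative prescribing without a limit at discharge, the only prescribing outcome ends there, and follow-up continues to 6 weeks with no visible capture of later prescriptions.

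Neither size nor direction can be fixed from the documents. On the assumed inputs, the apparent 33.3% reduction corresponds to 12.1% to 27.9% in total supply if the intervention arm is refilled more often (5% vs 20%, or 10% vs 30%). With equal rates of 5% or 10% it is 30.3% to 32.8%, with the pill difference unchanged. With 20% vs 10% it is 34.4% to 36.1%, so the bias reverses. These figures show sensitivity and are not estimates.

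Severity is low to moderate: this is a secondary outcome, it is partly covered by the consumption measures, and the sample size is unaffected. Uncertainty about direction is itself a reason to collect the data, because without them the trial cannot show which case applies.

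**What to change.** For Aim 2b, define the outcome as cumulative opioid prescribed, in MME, from discharge to the 6-week visit. This is the discharge prescription plus every later opioid prescription found in the medical record or reported when women are asked at the 2- and 6-week contacts. Keep the discharge quantity as a named component, and report the proportion with any further opioid prescription by arm. State that the 2- and 6-week pill counts start from total supply to date.

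The alternative is to limit Aim 2b and its hypothesis to the discharge prescription and to draw no conclusion about prescribing beyond it.

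The cost is two questions at contacts already planned and a chart check in the record system already used for screening. The HIPAA waiver in the checklist section covers prescreening only, and the information listed in section 25 does not name later prescriptions, so the authorization may need an added line. A local chart check will miss some outside prescribers, which is why the question to the patient is needed as well. The reported reduction in prescribing may turn out smaller.
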